5.1.6. Laboratory Tests

All tests listed in Table 3 below will be performed according to the Schedule of Visits and Assessments (Section 1.3) unless otherwise noted. No food restrictions are required for the collection of specimens. In addition, laboratory safety tests may be performed at various unscheduled time points, if deemed necessary by the Investigator.

Hematology	Serum Chemistry
Hemoglobin	Blood Urea Nitrogen
Hematocrit	Bilirubin (total and direct)
Total and differential leukocyte count	Alkaline phosphatase
Red blood cell count with indices and	Aspartate aminotransferase
morphology	Alanine aminotransferase
Platelet count	Albumin
	Sodium
	Potassium
	Chloride
	Glucose
	Creatinine
Urinalysis	Additional Tests
pH	Urine pregnancy test**
Specific gravity	(for females of child bearing potential only)
Protein*	Serum pregnancy test (hCG)***
Glucose	FSH test, (post menopausal) ***
Ketones	
Bilirubin	
Blood*	
Nitrite*	
Urobilinogen	
Leukocyte esterase*	

Table 3:Laboratory Tests

* If urinalysis is positive for protein, blood, nitrite and/or leukocyte esterase, a microscopic examination (for red blood cells, white blood cells, bacteria, casts, and epithelial cells) will be performed.

**At Baseline and Weeks 1, 2, and 4 for FOCBP only

*** At screening only

5.1.7. Patient Health Questionnaire depression scale (PHQ-8)

The PHQ-8 Assessment (Appendix 2) will be performed in adult subjects according to the Schedule of Visits and Assessments (Section 1.3).

PHQ-8 score is the sum of the responses for the 8 questions.

Five severity categories of depression are defined as follows:

- None Minimal depression (0 to 4)
- Mild depression (5 to 9)
- Moderate depression (10 to 14)

- Moderately severe depression (15 to 19)
- Severe depression (20 to 24)

A subject with a PHQ-8 score of 10-14 should be referred to a mental health professional for evaluation, regardless of the reason for their change in score.

A subject with a PHQ-8 score ≥ 15 should be immediately referred to a mental health professional, and Investigators in consultation with the mental health professional should consider interruption or discontinuation of the study drug.

5.1.8. Patient Health Questionnaire Depression Scale (Modified PHQ-A)

The Modified PHQ-A Assessment (Appendix 3) will be performed in adolescent subjects (12-17 years old, inclusive).

Modified PHQ-A score is the sum of the responses for five severity categories of depression defined as follows:

- None Minimal depression (0 to 4)
- Mild depression (5 to 9)
- Moderate depression (10 to 14)
- Moderately severe depression (15 to 19)
- Severe depression (20 to 24)

A subject with a modified PHQ-A score of 10-14 should be referred to a mental health professional for evaluation, regardless of the reason for their change in score.

A subject with a modified PHQ-A score ≥ 15 should be immediately referred to a mental health professional, and Investigators in consultation with the mental health professional should consider interruption or discontinuation of the study drug.

5.1.9. Children's Depression Inventory 2

The CDI-2 Assessment will be performed according to the Schedule of Visits and Assessments (Section 1.3) for subjects 6 to 11 years old, inclusive.

The CDI-2 quantifies depressive symptomatology using reports from children/adolescents, teachers, and parents or caregivers. It is recommended for use in initial evaluation and is appropriate when there is a need for an assessment and robust description of a child's depressive symptoms.

This study will use the CDI Parent Report Form. An example of the Parent report form is presented in Appendix 4.

A subject with a CDI-2 raw score of ≥ 21 for females and ≥ 22 for males should be referred to a mental health professional for evaluation.

A subject with a CDI-2 raw total score of \geq 32 should be referred to a mental health professional, and Investigators in consultation with the mental health professional should consider interruption or discontinuation of the study drug.

5.1.10. Columbia-Suicide Severity Rating Scale (C-SSRS)

C-SSRS Assessments will be performed according to the Schedule of Visits and Assessments (Section 1.3) for subjects 12-years old and older.

The administration schedule of the C-SSRS will be:

- The "Baseline/Screening" version (Appendix 5) will be used at Screening to provide a pre-treatment assessment.
- On all subsequent visits, the "Since Last Visit" version (Appendix 6) will be used (Baseline/Day 1, Week 1/Day 8, Week 2/Day 15 or Week 4/Day 29).
- A score greater than 0 at the Screening or Baseline visit in suicidal ideation may indicate the need for mental health intervention. The investigator should not enroll the subject in the study.
- Any score greater than 0 in the suicidal ideation score may indicate the need for mental health intervention. The Investigator should give consideration for the subject to discontinue from the study drug and prompt referral to an identified mental health professional and/or an appropriate emergency room. The Medical Monitor should be contacted.

The C-SSRS administer will be trained via the C-SSRS training video. A training certificate for the administer(s) will be on file in the trial master file at the site.

The Investigator must review the completed C-SSRS. A qualified mental health care provider must be available, immediately if needed, to refer the subject for further evaluation.

5.1.11. Local Tolerability Assessment

The Investigator Local Tolerability Assessment will be performed according to the Schedule of Visits and Assessments (Section 1.3).

Application site reactions will be graded at each timepoint. Irritation reactions are graded using the scale detailed in the following section (Berger 1982). Reactions at the site of product application, which may occur post-Baseline, should be differentiated from the preexisting inflammation associated with the subject's atopic dermatitis.

The investigator assessments will be conducted by the investigator or a properly trained and designated subinvestigator prior to study drug application in the clinic.

Dermal Response

- 0. no evidence of irritation
- 1. minimal erythema, barely perceptible
- 2. definite erythema, readily visible; minimal edema or minimal papular response
- 3. erythema and papules

- 4. definite edema
- 5. erythema, edema and papules
- 6. vesicular eruption
- 7. strong reaction spreading beyond application site

Other Effects

- A. = slight glazed appearance
- B. = marked glazing
- C. = glazing with peeling and cracking
- D = glazing with fissures
- E. = film of dried serous exudates
- F. = small petechial erosions and/or scabs
- G_{\cdot} = no other effects

The Subject Local Tolerability Assessment will be performed according to the Schedule of Visits and Assessments (Section 1.3).

Grade	Sensation Following Drug Application	
0 (none)	No sensation	
1 (mild)	Slight warm, tingling sensation; not really bothersome	
2 (moderate)	Definite warm, tingling sensation that is somewhat bothersome	
3 (severe)	Hot, tingling/stinging sensation that has caused definite discomfort	

The subject will assess burning/stinging (0-3 score):

This assessment will be administered by the site 10 to 15 minutes after study drug application in the clinic at Baseline and at every clinic visit.

• Note: for subject burning stinging assessment at Day 29, subjects will provide a recall assessment of burning/stinging experienced post drug application on the previous day (Day 28).

5.1.12. Adverse Events

Adverse events (AEs) will be collected and assessed throughout the study according to the Schedule of Visits and Assessments (Section 1.3). The Investigator is responsible for ensuring that all adverse events observed by the clinical staff or reported by the subject that occur after the first application of investigational product through the end of the study are recorded in the subject's medical record and the eCRF.

The Investigator is responsible for ensuring that all serious adverse events observed by the clinical staff or reported by the subject that occur after signing of the informed consent through 30 days after the last day of the application of the investigational product or the end of study (whichever is later) are recorded in the subject's medical record and are submitted per SAE reporting requirements (Section 5.7.5).

AEs (whether serious or non-serious) and clinically significant abnormal laboratory test value(s) will be evaluated by the PI and treated and/or followed up for up to 30 days after end of treatment or until the symptoms or value(s) return to normal, or acceptable levels, as judged by the PI. Refer Section 5.7 for further details on Adverse Events.

5.2. Efficacy Evaluations

For efficacy evaluation subjects will have $\geq 3\%$ BSA of AD involvement (excluding the scalp, palms, soles). Palms and soles may be treated with investigational product in this study, but will not be counted towards vIGA-AD, EASI, or BSA assessments. EASI is evaluated for the entire body except the scalp, palms, and soles..

5.2.1. Validated Investigator Global Assessment Scale for Atopic Dermatitis

Validated Investigator Global Assessment scale for Atopic Dermatitis (vIGA-AD) assessments should be completed prior to other physician assessments.

vIGA-AD assessment will be performed according to the Schedule of Visits and Assessments (Section 1.3). The vIGA-AD is a static evaluation of qualitative overall AD severity. This global assessment scale is an ordinal scale with five severity grades (reported only in integers of 0 to 4). Each grade is defined by a distinct and clinically relevant morphologic description that minimizes inter-observer variability (see Appendix 7). vIGA-AD is evaluated for the entire body except the scalp, palms, and soles.

Note: All atopic dermatitis lesions on a subject will be treated including the face, trunk, genitals/skin folds, or limbs (excluding the scalp). The palms and soles will be treated but will not be counted towards any measurements of efficacy (EASI, vIGA-AD, BSA).

Every effort must be made for the same Evaluator to complete the IGA for the subject at every study visit.

IGA will be assessed at clinic visits prior to the subject applying Investigational Product at the site.

5.2.2. Eczema Area and Severity Index (EASI)

EASI scores (Hanifin 2001) will be performed according to the Schedule of Visits and Assessments (Section 1.3)

Four anatomic sites—head, upper extremities, trunk, and lower extremities—are assessed for erythema, induration/infiltration (papules), excoriation, and lichenification as seen on the day of the examination. The severity of each sign is assessed using a 4-point scale (half steps are allowed; e.g. 0.5, 1.5 and 2.5):

- 0 = none
- 1 = mild
- 2 = moderate
- 3 =severe

The area affected by atopic dermatitis within a given anatomic site is estimated as a percentage of the total area of that anatomic site and assigned a numerical value according to the degree of atopic dermatitis involvement as follows:

- 0 = no involvement
- 1 = 1-9%
- 2 = 10-29%
- 3 = 30-49%
- 4 = 50-69%
- 5 = 70-89%
- 6 = 90**-**100%

The EASI score is obtained by using the formula below for subjects ≥ 8 years old:

$$EASI = 0.1 (E_h + I_h + Ex_h + L_h) A_h + 0.2 (E_u + I_u + Ex_u + L_u) A_u + 0.3 (E_t + I_t + Ex_t + L_t) A_t + 0.4 (E_l + I_l + Ex_l + L_l) A_l$$

The EASI score is obtained by using the formula below for subjects <8 years old:

$$EASI = 0.2 (E_h + I_h + Ex_h + L_h) A_h + 0.2 (E_u + I_u + Ex_u + L_u) A_u + 0.3 (E_l + I_l + Ex_l + L_l) A_l + 0.3 (E_l + I_l + Ex_l + L_l) A_l$$

Where E, I, Ex, L, and A denote erythema, induration, excoriation, lichenification and area, respectively, and h, u, t, and l denote head, upper extremities, trunk, and lower extremities, respectively.

Note: Palms and soles may be treated with investigational product in this study, but will not be counted towards IGA, EASI, or BSA assessments. EASI is evaluated for the entire body except the scalp, palms, and soles.

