1.3. Schedule of Visits and Assessments

- ^a Limited physical examination: skin (including assessment of Fitzpatrick skin type at Screening only), lungs, and heart only
- ^b To be collected at Screening, Baseline/Day 1, and Week 4/Day 29. For subjects <18 years of age, if Baseline/Day 1 is within 3 weeks of Screening, the Screening results will be utilized.
- ^c Height will be collected at Screening only. Weight should be obtained using a calibrated weight scale and the same scale should be used for a subject throughout the duration of the study. The subject should remove shoes and heavy clothing (sweaters or jackets), and empty pockets. The subject should stand with both feet in the center of the scale with their arms at their side and hold still. Record the weight to the nearest decimal fraction (for example, 25.1 kilograms). For subjects <18 years of age, measure the weight in triplicate and report the average weight in EDC. A 5% or greater weight loss (whether or not intentional or other explained) should be reported to the medical monitor.
- ^d The vIGA-AD assessment will be a 5-point scale ranging from clear (0) to severe (4) and is evaluated for the entire body except the scalp, palms, and soles. EASI takes into account overall severity of erythema, infiltration/papulation, excoriation, and lichenification, in addition to extent of BSA affected. The 4 clinical signs will be graded on a 4-point scale (0 [absent] to 3 [severe]) for 4 body regions (head and neck, upper extremities, lower extremities, and trunk). Total EASI score will be calculated as a sum of scores of all 4 body regions. EASI total score will range from 0 (absent) to 72 (severe). Total BSA affected by AD will be determined for all body surfaces except the scalp, palms and soles. **The vIGA-AD assessment should be completed prior to other physician assessments**. SCORAD total score will range between 0 and 103.
- Subjects will self-assess their pruritus at home on a daily basis starting 7 days prior to the Baseline/Day 1 visit, and then every day thereafter. WI-NRS score will be determined by the subject assessing worst itch over the past 24 hours. The scale is from 0 (no itch) to 10 (worst itch) and this value will be recorded by the subject each day.
- ^f POEM will be completed by all subjects either by self or by proxy completion (for children unable to read and/or understand the POEM questionnaire, the parent/guardian/caregiver will complete the questionnaire).

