5.5 Derived Variables

All questionnaire scores will be derived by Biostatistics in the ADaM datasets using the formulas defined below, even if calculated scores are present in the EDC database. All pre-calculated scores will be ignored for analysis.

- vIGA-AD Success = vIGA-AD of 'Clear' (0) or 'Almost Clear' (1) plus at least a 2-grade improvement from Baseline.
- Average weekly WI-NRS = Average weekly of the WI-NRS pruritus scores will be
 calculated as the sum of the daily WI-NRS scores reported during a specific week (in a 7day period) of the study divided by the number of days with non-missing scores for that
 week. A minimum of 4 days of observations are needed to calculate average weekly WINRS. Otherwise, the corresponding average weekly WI-NRS will be considered missing.

	STATISTICAL ANALYSIS PLAN, Version 1.0
Protocol Number: ARQ-151-312	Sponsor: Arcutis Biotherapeutics, Inc.

The average weekly WI-NRS results will be presented for analysis visits i.e., Baseline, Week 1, Week 2, Week 3, and Week 4 (see Table 1 Table 4 for the analysis window).

• WI-NRS 4-point reduction = achievement of a 4- point reduction in average weekly WI-NRS pruritus score compared to average weekly WI-NRS baseline, calculated only for the subjects ≥12 years old with average weekly WI-NRS score of ≥ 4 at baseline.

$$\begin{split} \bullet \quad & \text{EASI total score} = 0.1 \; (E_h + I_h + E_{Xh} + L_h) \; A_h + 0.2 \; (E_u + I_u + E_{Xu} + L_u) \; A_u \\ & \quad + 0.3 \; (E_t + I_t + E_{Xt} + L_t) \; A_t + 0.4 \; (E_l + I_l + E_{Xl} + L_l) \; A_l \\ & \quad \text{for subjects $`\geq 8$ years old} \\ & \quad \text{and} \\ & \quad 0.2 \; (E_h + I_h + E_{Xh} + L_h) \; A_h + 0.2 \; (E_u + I_u + E_{Xu} + L_u) \; A_u \\ & \quad + 0.3 \; (E_t + I_t + E_{Xt} + L_t) \; A_t + 0.3 \; (E_l + I_l + E_{Xl} + L_l) \; A_l \\ & \quad \text{for subjects < 8 years old} \end{split}$$

where E, I, Ex, L, and A denote erythema, induration, excoriation, lichenification, and area, respectively, and h, u, t, and l denote head, upper extremities, trunk, and lower extremities, respectively. If a subject turns 8 years old during the study, the formula used at Screening will continue to be used through the study duration of the subject's participation in the study. Scalp, palms, and soles may be treated with investigational product in this study but will be excluded from the EASI assessment.

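### As printed, the protocol's EASI formula for children under 8 counts the legs twice and omits the trunk; applied literally, it could misjudge the EASI ≥5 entry criterion at ages 6–7

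*Protocol*

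**What the plan says.** Protocol 5.2.2 prints two formulas, one for subjects aged 8 or more and one for those under 8.

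- **Age 8 and over.** The last two terms are "0.3 (E_t + I_t + Ex_t + L_t) A_t + 0.4 (E_l + I_l + Ex_l + L_l) A_l": trunk at 0.3, lower extremities at 0.4.
- **Under 8.** Head and upper extremities each carry 0.2. The last two terms are "0.3 (E_l + I_l + Ex_l + L_l) A_l + 0.3 (E_l + I_l + Ex_l + L_l) A_l": the lower-extremity term twice, with no trunk term.

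The surrounding text includes the trunk at every age. Section 5.2.2 opens with "Four anatomic sites—head, upper extremities, trunk, and lower extremities—are assessed for erythema" and makes no exception for age. Its symbol key states that "h, u, t, and l denote head, upper extremities, trunk, and lower extremities, respectively". Footnote d to the schedule in Protocol 1.3 says "Total EASI score will be calculated as a sum of scores of all 4 body regions", names the trunk as one of the four, and gives a range of 0 to 72.

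SAP 5.5 gives the under-8 formula as 0.2 head, 0.2 upper extremities, 0.3 trunk, 0.3 lower extremities. It adds: "If a subject turns 8 years old during the study, the formula used at Screening will continue to be used". It also says that scores are derived afresh from its own formulas and that any totals already in the database are disregarded.

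Inclusion criterion 5 (Protocol 1.1 and 4.5.1) requires EASI of at least 5, assessed over the whole body apart from scalp, palms and soles. It cites no formula. The lower age limit is 6 years.

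**The concern.** Section 5.2.2 holds the only EASI formula in the protocol for 6–7 year-olds, and EASI decides entry. A term printed twice, beside a symbol key that defines a trunk subscript the formula never uses, is an internal contradiction. It is not a matter of missing detail.

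The SAP governs analysis and reporting, so its correct formula does not by itself reach the screening decision. If a site worksheet or the electronic data-capture (EDC) system was built from the printed line, a child with mainly trunk disease could be turned away although eligible. A child with mainly leg disease could be admitted with an EASI below 5. Protocol 7.6 allows no waivers of entry criteria, so an admission of that kind would be an eligibility deviation, and nobody would see it unless the score was recomputed.

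**Working it through.** **Inputs.** Each region has four signs scored 0–3, so the sign sum runs from 0 to 12, and an area score of 0–6 (Protocol 5.2.2). Write H, U, T and L for sign sum × area score in the head, upper extremities, trunk and lower extremities. Each product has a maximum of 12 × 6 = 72.

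**Formulas for ages under 8.**

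- Protocol 5.2.2 as printed: 0.2H + 0.2U + 0.3L + 0.3L = 0.2H + 0.2U + 0.6L
- SAP 5.5: 0.2H + 0.2U + 0.3T + 0.3L
- Printed minus SAP: 0.3 × (L − T)

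**The plan's own figure.** The stated maximum is 72. The printed formula gives (0.2 + 0.2 + 0.3 + 0.3) × 72 = 72. The SAP under-8 formula also gives 72, and so does the formula for age 8 and over: (0.1 + 0.2 + 0.3 + 0.4) × 72. All the weights sum to 1.0, so the range check passes for every version and cannot reveal the missing trunk term.

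**Worked cases.** The products are illustrative assumptions, not trial data.

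| Pattern (H, U, T, L) | SAP 5.5 | Protocol as printed | Effect at EASI ≥5 |
|---|---|---|---|
| Trunk only, sign sum 6, area 3: (0, 0, 18, 0) | 0.3 × 18 = 5.4 | 0 | wrongly excluded |
| Legs only, sign sum 5, area 2: (0, 0, 0, 10) | 0.3 × 10 = 3.0 | 0.6 × 10 = 6.0 | wrongly admitted |
| Arms and mainly trunk: (0, 8, 12, 2) | 1.6 + 3.6 + 0.6 = 5.8 | 1.6 + 1.2 = 2.8 | wrongly excluded |
| Arms and mainly legs: (0, 8, 2, 8) | 1.6 + 0.6 + 2.4 = 4.6 | 1.6 + 4.8 = 6.4 | wrongly admitted |
| Trunk equal to legs: (4, 6, 12, 12) | 0.8 + 1.2 + 3.6 + 3.6 = 9.2 | 0.8 + 1.2 + 7.2 = 9.2 | none |

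Under the printed line, trunk-only disease always scores 0. Legs-only disease reaches 5 at a product of 5 / 0.6 = 8.33 instead of 5 / 0.3 = 16.67.

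**Who is affected.** Only children aged 6 or 7 at Screening are affected. SAP 5.5 keeps the Screening formula for a child who turns 8 during the study.

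**Which analyses are affected.** None. SAP 5.5 lists the EASI total among the derived scores, and SAP 12.2 treats EASI as a questionnaire, so the re-derivation rule covers it. EASI-75, the other EASI thresholds and the change scores therefore all use the trunk term. The primary endpoint is vIGA-AD success and does not use EASI.

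**The case against.** The strongest objection is that the page itself may be right. The formula was read from a PDF by a program, and the whole point turns on a subscript t or l, which are easily confused. That possibility stands and cannot be settled from the text. Two facts weigh against it: all five symbols in the term carry l, and the same reading gave all five t subscripts correctly in the formula just above. The text favours a real error, but the source page has to be checked.

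Second, a reader might infer that the entry test did give wrong scores for 6–7 year-olds. The documents do not support that. Criterion 5 cites no formula, and nothing says which formula the sites or the data-capture system used at screening. The four-site list, the symbol key and the schedule footnote all tell an investigator to include the trunk. A child with visible trunk disease who must also have at least 3% body surface involvement, yet scores 0, would prompt a question. This part of the objection stands, so the consequence is conditional.

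Third, the protocol supplied is the Original, while SAP section 1 says it follows Amendment 3 dated 23 May 2022. Whether the line survives in the amendment cannot be seen. This also stands, and it determines the order of the fix.

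**Conclusion.** Wrong as written, and of minor severity. In the supplied protocol text the under-8 EASI formula repeats the lower-extremity term and omits the trunk, against its own section, the schedule footnote and SAP 5.5.

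If the line was applied literally, the screening score for a 6–7 year-old is off by 0.3 × (leg product − trunk product), and the EASI ≥5 decision can go wrong either way. The error is zero when the two products are equal, so not every child's score would be wrong.

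This rests on two conditions that the documents leave open: that the printed page matches the supplied text, and that a site or EDC calculator used it. The documents do not give the number of 6–7 year-olds. They give no distribution of disease by region either, so any misclassification rate would rest on assumed distributions, and none is offered here.

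A reader might also infer that EASI-75 is compromised. It is not, because the SAP re-derives every EASI total with the trunk term.

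**What to change.** 1. Check the source page of Protocol 5.2.2 and the same section in the current amendment.
2. If the error is there, replace the third term of the under-8 formula with the trunk term, `0.3 (E_t + I_t + Ex_t + L_t) A_t`, to match SAP 5.5.
3. Confirm which formula the site or EDC calculator used for screening EASI in children under 8.
4. Only if the printed version was used, recompute screening and baseline EASI from the item scores for enrolled 6–7 year-olds. List those below 5 as eligibility deviations before the major-deviation list that defines the Per Protocol set is fixed (SAP 4.3 and 7.2).

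The cost is a one-term text correction and one query about the calculator. Step 4, if needed, uses item scores already collected, and its only downside is that a few children may be listed as entry deviations. If the calculator already includes the trunk, the matter closes as a text correction.
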